5.1.2 Analysis Population

The analysis population will include all patients who provide consent, are enrolled into the study, and have data available for 1 or more of the primary and secondary endpoints.

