10.4.1 Analyses of Study Endpoints

For the primary endpoint, the proportion of CS patients who are at least somewhat satisfied with their overall symptom control at 6 months, a point estimate and the corresponding 95% CLs will be calculated. Secondarily, a point estimate and corresponding 95% CLs will be calculated for the proportion of CS patients who are very satisfied with their overall symptom control at 6 months. The 95% CLs will be unadjusted and based on the assumption of approximate normal distribution. Missing data will not be imputed in the main analysis of the primary endpoint. As a sensitivity analysis, a patient with a missing response at 6 months will be imputed as a non-responder. This approach corresponds to non-responder imputation.

In addition to the point estimates and 95% CLs for the primary endpoint, the frequency distribution of the categorical responses, on a 5-point Likert scale, to patient satisfaction with overall symptom control at 6 months will be presented. The patient satisfaction measure will also be summarized as an ordinal variable with a value of 1 corresponding to “very dissatisfied” up to 5 corresponding to “very satisfied”.

All the secondary endpoints correspond to proportions and will be summarized through point estimates and 95% CLs, as described above for the primary endpoint. Frequency distributions of the categorical responses and summary statistics of the corresponding ordinal values of the categories will be presented. The handling of patients with a response of “not applicable” to patient satisfaction with CS-related diarrhea control or patient satisfaction with CS-related flushing control in the analysis will be described in the SAP.

The 4 WPAI-SHP scores at Baseline and month 6 will be summarized, as well as the change from Baseline to month 6.

The incidences of at least 1 CS-related hospitalization, at least 1 CS-related ER visit, and mortality after Baseline will be calculated at each 6-month interval. Kaplan-Meier estimates of each time-to-event variable, including quartiles, medians, and their corresponding 95% CLs, will be presented. The association or relationship between the primary endpoint and each long-term health outcome will be evaluated through descriptive statistics and the use of statistical models, as appropriate. Any statistical models that will be used and the appropriateness and/or limitations of their use will be described in the SAP.

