2.3 Study Endpoints

2.3.1 *Primary Endpoint*

The primary endpoint of the study is the proportion of patients with CS who are satisfied with their overall symptom control, 6 months after initiating treatment with telotristat ethyl (XERMELO).

2.3.2 *Secondary Endpoints*

The following secondary endpoints will be assessed 6 months after initiating treatment with telotristat ethyl (XERMELO):

- The proportion of patients reporting satisfaction of CS-related diarrhea control
- The proportion of patients reporting satisfaction of CS-related flushing control
- The proportion of patients reporting reduction in rescue SSA use
- The proportion of patients reporting reduction in the dose of long-acting SSA injection
- The proportion of patients reporting reduction in the frequency of long-acting SSA injection
- The proportion of patients reporting an overall improvement in CS control after initiating XERMELO based on PGIC

- The proportions of patients who had reduction in work-related absenteeism, presenteeism, activity impairment, and overall productivity loss after initiating XERMELO based on the WPAI-SHP
- The proportion of patients reporting weight gain

2.3.3 *Other Endpoints*

Other endpoints include incidence of CS-related hospitalizations, incidence of CS-related emergency room (ER) visits, and incidence of mortality at 6-month intervals for up to 3 years after initiation of treatment with XERMELO.

Another endpoint, not described in the protocol, is the proportion of patients with a reduction in the number of bowel movements. This endpoint will be assessed at the 6-month Follow-up after initiation of treatment with XERMELO.

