2.4 Sample Size Determination

The sample size was derived by satisfying design assumptions for the primary study endpoint of the proportion of patients with CS who are satisfied with their overall symptom control, 6 months after initiating treatment with telotristat ethyl (XERMELO). Of specific interest is the proportion of patients with CS who are at least somewhat satisfied with their control of CS at 6 months, defined as those patients with a response of either "very satisfied" or "somewhat satisfied". This proportion will be estimated as x/n , where x is the number of patients in the study who are either "Very satisfied" or "Somewhat satisfied", and n is the number of patients with a non-missing response for the primary endpoint. Two-sided 95% confidence limits (CLs) will be calculated for this proportion using normal approximation. The true proportion may be approximately 50%; hence, an expected proportion of 50% was used in the sample size calculation as it requires the largest n . It is desired for the proportion to be known with a precision, ω , of 5%, that is, for the CLs to be $(x/n) \pm \omega$. Based on the expected proportion of 50% and the precision requirement of 5%, $n = 385$ patients are needed to have a non-missing response for the primary endpoint. Assuming that 40% of the patients who participate in the study will drop out prior to the 6-month survey, then a minimum of $N = 643$ patients, with CS who initiate treatment with XERMELO, should be entered into the study.

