4.1.2 Baseline Analysis

After the last patient enrolled in the study completes a Baseline questionnaire [REDACTED] an analysis will be performed to summarize the burden of CS for all patients (n = 643) at the time that XERMELO was initiated as a new treatment. This analysis will include summaries of all questionnaire items as well as interim analyses of all primary and secondary endpoints for patients who have completed the 6-month Follow-up.

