5.1.4 Primary and Secondary Endpoint Analyses

Responses to questionnaire items related to the primary and secondary endpoints will be summarized as categorical variables, as described in [Section 5.1.1](#). Items having ordinal response scales consisting of at least 5 categories will also be summarized as ordinal variables. Estimates of proportions for all primary and secondary endpoints at the initial 6-month Follow-up will be accompanied by 2-sided 95% CLs based on the normal distribution approximation.

For estimation of the proportions for the primary and secondary endpoints, patients will be categorized based on their responses to the corresponding questionnaire items as described in Table 1. Responses of "Not applicable" will be excluded from the denominator for computation of each proportion. Missing data will not be imputed, with the exception of a sensitivity analysis on the primary endpoint, whereby a patient with a missing response will be imputed as a non-responder (ie, neither "Very satisfied" nor "Somewhat satisfied"). Some endpoints will have supplemental/sensitivity analyses in addition to the main analysis, and specifications for those analyses are also shown in Table 1.

In addition to the proportions of patients reporting reduction from Baseline in the 4 domains of the WPAI-SHP, domain scores will be summarized at Baseline and at the initial 6-month Follow-up. The change in score for each domain over this 6-month interval will also be summarized as a continuous variable.

Table 1. Primary and Secondary Endpoint Definitions

	Definition for Main Analysis	Definition for Supplemental Analyses
Primary Endpoint (proportion of patients at 6 months after initiating treatment with XERMELO)		
Satisfaction with overall control of CS symptoms	“Very satisfied” or “Somewhat satisfied”	
 “Very satisfied” only [REDACTED]
Secondary Endpoints (proportions of patients at 6 months after initiating treatment with XERMELO)		
Satisfaction with control of CS-related diarrhea	“Very satisfied” or “Somewhat satisfied”	“Very satisfied” only
Satisfaction with control of CS-related flushing	“Very satisfied” or “Somewhat satisfied”	“Very satisfied” only
Reduction in rescue SSA use	“Less frequent”	N/A
Reduction in dose of long-acting SSAs	“Decreased”	N/A
Reduction in frequency of long-acting SSA injection	“Decreased”	N/A

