5.1.5 Other Endpoint Analyses

5.1.5.1 Analyses of Incidence of Emergency Room Visits, Hospitalizations, and Mortality

Incidence proportions for patients with at least 1 ER visit, at least 1 hospitalization, and mortality during each 6-month Follow-up interval will be reported along with 95% CLs. The denominator for each incidence proportion will be the number of patients enrolled in the

study at the beginning of that particular 6-month interval who also provide a non-missing response to the questionnaire item for each type of event.

The time to the first occurrence of a CS-related ER visit, time to the first occurrence of a CS-related hospitalization, time to the first occurrence of a CS-related ER visit or hospitalization, and time to mortality will be analyzed using the nonparametric Turnbull estimation method ([Turnbull, 1976](#)) for interval-censored data available in SAS PROC ICLIFETEST for each 6-month interval during Follow-up. These tables will display the number of patients still at risk at the beginning of the interval along with the number of events and censored observations within each interval. Estimates of the survival probability (the proportion of patients without the event) will be provided for the upper boundary of each interval, and these probabilities will also be displayed as figures. Estimated quartiles for event-free time (with 95% CLs) will be reported.

If death dates are available for the analysis of mortality, this analysis will be performed using the Kaplan-Meier method instead of the Turnbull method. Estimated quartiles for survival time (with 95% CLs) will be reported, and estimated survival probabilities will be displayed as Kaplan-Meier curves.

Details for all ER visits and hospitalizations, including the reason for the visit or hospitalization, will be provided in data listings.

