5.2 Missing Data

No imputations will be performed, except as noted for the sensitivity analysis for the primary endpoint as described in Table 1 ([Section 5.1.4](#)). In all other cases, missing data will be excluded and variables will be analyzed using the available observed data.

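### Taken literally, the only analysis population leaves out patients who drop out before the 6-month survey (40% planned), which contradicts the Baseline analysis and nearly empties the non-responder imputation

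*SAP*

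**What the plan says.** **Population.** SAP 5.1.2 and protocol 10.2 give the same definition, and no other analysis set is defined. Patients must have consented, be enrolled, and "have data available for 1 or more of the primary and secondary endpoints".

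**Endpoint timing.** SAP 2.3 and protocol 10.3.1 assess the primary and all secondary endpoints 6 months after starting XERMELO.

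**Dropout.** SAP 2.4 sizes the study as follows: "Assuming that 40% of the patients who participate in the study will drop out prior to the 6-month survey". Stopping XERMELO ends participation (protocol 5.1.1, SAP 3.2.7). The survey link is disabled after a reported status change (protocol 5.1), and one missed survey in a year withdraws the patient (protocol 6.3).

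**Imputation.** Protocol 10.4.1: "As a sensitivity analysis, a patient with a missing response at 6 months will be imputed as a non-responder". SAP 5.1.4 has a "sensitivity analysis on the primary endpoint, whereby a patient with a missing response will be imputed as a non-responder". SAP 5.2 adds: "No imputations will be performed, except as noted for the sensitivity analysis for the primary endpoint as described in Table 1". In that table, one bullet in the supplemental cell for the primary endpoint is redacted.

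**Baseline analysis.** SAP 4.1.2 runs it once the last enrolled patient has completed the Baseline questionnaire and covers all patients, with n given as 643.

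**The concern.** The population rule and two of the planned analyses call for different patients. Someone who leaves before month 6 has no value for any primary or secondary endpoint, so SAP 5.1.2 removes that person. The imputation sentences, read naturally, are there to deal with that same person. The Baseline analysis includes that person explicitly, along with recent enrollees who cannot yet have 6-month data.

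The imputation is the plan's only visible check on missing primary data. If SAP 5.1.2 governs it, the check reaches only patients who returned the survey and left the satisfaction item blank, and it says nothing about those who left.

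The leavers matter because of the plan's own reasoning. Protocol 3.2 assumes that satisfied patients stay on XERMELO, and stopping XERMELO ends participation. Missing responses are therefore likely to come more often from less satisfied patients. Two programmers working from the same text could report very different sensitivity results.

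**Working it through.** **1. The plan's sample size.** Inputs from SAP 2.4: expected proportion 0.50, half-width 0.05, two-sided 95% limits by normal approximation, 40% dropout.

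- n = 1.96² × 0.5 × 0.5 / 0.05² = 384.15, rounded up to 385, as stated.
- N = 385 / (1 − 0.40) = 641.7, rounded up to 642. The SAP states 643, one patient more, which is immaterial.

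**2. Patients without a primary response.** 643 − 385 = 258, or 40.1% of those enrolled.

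**3. Main estimate.** Satisfied: 0.5 × 385 = 192.5, taken as 192. Then 192/385 = 49.9%, with 95% limits p ± 1.96 × √(p(1 − p)/n) = 44.9% to 54.9%.

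**4. Imputation over all enrolled.** 192/643 = 29.9% (26.3% to 33.4%). This is the same however the 258 divide between leavers and item-skippers.

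**5. Imputation if SAP 5.1.2 governs.** Only returned surveys count. Let m be the share of returned surveys with the item blank. The documents give no value for m, so it is an assumption. Returned surveys = 385/(1 − m), and the imputed proportion = 192/returned.

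| Assumed m | Returned surveys | Item-skippers | Leavers outside the check | Imputed proportion | Gap to 29.9% (points) |
|---|---|---|---|---|---|
| 0% | 385 | 0 | 258 | 49.9% | 20.0 |
| 2% | 393 | 8 | 250 | 48.9% | 19.0 |
| 5% | 405 | 20 | 238 | 47.4% | 17.5 |
| 10% | 428 | 43 | 215 | 44.9% | 15.0 |

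At m = 0% the imputation changes nothing. Even at 10%, 215 of the 258 missing patients lie outside it.

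**6. A different satisfaction level.** If 70% of responders were satisfied (assumed; 0.7 × 385 = 269.5), imputing over all enrolled gives 269.5/643 = 41.9%. The literal population gives 70.0% with no skippers and 269.5/405 = 66.5% with 20. The gap is then 28.1 or 24.6 points, so the 50% case does not overstate it.

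**7. Baseline analysis.** No arithmetic is needed. At planned dropout the population in SAP 5.1.2 cannot number 643. When this analysis is run, patients enrolled in the previous six months cannot have a 6-month endpoint.

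**The case against.** The strongest objection is the redaction. SAP 5.1.4 and 5.2 both point to Table 1 for the imputation, and the hidden bullet may be its specification, with a denominator. Redacted text cannot be treated as missing. That stands, and the fix is conditional on it. It would not settle everything: SAP 5.1.2 and protocol 10.2 would still contradict such an entry, and the Baseline conflict does not depend on it.

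Second, a specific sentence usually overrides a general one, so the imputation would naturally cover dropouts and give 29.9%. This is a fair reading and probably the intended one, but the visible text does not state it. SAP 5.1.5.1 shows that the authors wrote out a denominator where they wanted a particular one.

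Third, satisfaction and the WPAI-SHP are also collected at Baseline. If those counted as endpoint data, most patients would be kept. The documents do not say so. Baseline satisfaction concerns control before XERMELO, the WPAI-SHP endpoints are reductions that need the 6-month score, and SAP 2.3 fixes the timing at 6 months.

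Fourth, the impact is limited. The main estimate is unaffected, all analyses are descriptive, and the figure over all enrolled can be worked out from the disposition table and the response counts. The SAP also provides a variable specification document, independent programming checks and a dry run. All this is true and limits the severity. But a figure a reader can work out is not a prespecified analysis, and those checks do not settle an ambiguous rule.

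Fifth, the 40% is not split by cause, and patients also leave through death, missed surveys or loss to follow-up. So the lower satisfaction of leavers is an inference from the plan's rationale, not an established fact.

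**Conclusion.** The concern holds and should be fixed before the primary-endpoint analysis. As written, the single population excludes about 258 of 643 patients at planned dropout. That directly contradicts the Baseline analysis set, and if applied it leaves the only visible missing-data check nearly empty. The two readings of the imputation give 29.9% and 44.9% to 49.9%, a gap of 15 to 20 points, which is three to four times the 5-point precision the study was sized for.

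The size rests on the plan's figures (643 enrolled, 385 responses, 50% satisfied) and on an assumed skip rate of 0% to 10%. It also supposes that the redacted Table 1 bullet does not already name the denominator. Confidence is medium for that reason. The complete-case main estimate is not in question.

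**What to change.** - State in SAP 5.1.2 and 5.1.4, and in protocol 10.2 and 10.4.1, that the non-responder imputation uses all enrolled patients whose 6-month survey window has closed at the data cut, whether or not they have other endpoint data. The window condition keeps patients who are not yet due from being counted as failures at interim analyses.
- Label the result a worst-case bound and show the number of imputed patients by reason for discontinuation.
- State that the Baseline analysis is not restricted by SAP 5.1.2.
- Leave the complete-case main estimate as it is.
- If the redacted Table 1 bullet already sets this denominator, align only SAP 5.1.2 and protocol 10.2 with it.

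The cost is a few sentences, plus IRB approval of the protocol wording (protocol 11.4). No new data are needed, because enrolment, discontinuation and reasons are already planned for the disposition table (SAP 5.1.3.1). If the narrow reading was intended, the sensitivity figure will look much less favourable, hence the worst-case label.

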5.1.3 Summary Analyses

5.1.3.1 Patient Disposition

For each analysis, current patient disposition as of the database lock date will be summarized in tabular format. This table will report the number of completed Baseline and Follow-up questionnaires, the number and percentage of enrolled patients who discontinued the study after each Follow-up time point and overall, and the reasons for study discontinuation.

5.1.3.2 Demographics, Medical History, and Carcinoid Syndrome Treatments

Patient demographics and medical history information collected at Baseline, including prior treatments received for CS, will be summarized in separate tables. Age will be summarized both as a continuous variable and as a categorical variable (18-30 years, 31-40 years, 41-50 years, 51-64 years, 65 years or older, 75 years or older).

Information on treatments received for CS during study Follow-up, including changes in frequency and dose for short- and long-acting SSAs and additional treatments for CS ([Section 3.2.2](#)), will be summarized in tabular format for each Follow-up time point.

5.1.4 Primary and Secondary Endpoint Analyses

Responses to questionnaire items related to the primary and secondary endpoints will be summarized as categorical variables, as described in [Section 5.1.1](#). Items having ordinal response scales consisting of at least 5 categories will also be summarized as ordinal variables. Estimates of proportions for all primary and secondary endpoints at the initial 6-month Follow-up will be accompanied by 2-sided 95% CLs based on the normal distribution approximation.

For estimation of the proportions for the primary and secondary endpoints, patients will be categorized based on their responses to the corresponding questionnaire items as described in Table 1. Responses of "Not applicable" will be excluded from the denominator for computation of each proportion. Missing data will not be imputed, with the exception of a sensitivity analysis on the primary endpoint, whereby a patient with a missing response will be imputed as a non-responder (ie, neither "Very satisfied" nor "Somewhat satisfied"). Some endpoints will have supplemental/sensitivity analyses in addition to the main analysis, and specifications for those analyses are also shown in Table 1.

In addition to the proportions of patients reporting reduction from Baseline in the 4 domains of the WPAI-SHP, domain scores will be summarized at Baseline and at the initial 6-month Follow-up. The change in score for each domain over this 6-month interval will also be summarized as a continuous variable.

Table 1. Primary and Secondary Endpoint Definitions

	Definition for Main Analysis	Definition for Supplemental Analyses
Primary Endpoint (proportion of patients at 6 months after initiating treatment with XERMELO)		
Satisfaction with overall control of CS symptoms	“Very satisfied” or “Somewhat satisfied”	
 “Very satisfied” only [REDACTED]
Secondary Endpoints (proportions of patients at 6 months after initiating treatment with XERMELO)		
Satisfaction with control of CS-related diarrhea	“Very satisfied” or “Somewhat satisfied”	“Very satisfied” only
Satisfaction with control of CS-related flushing	“Very satisfied” or “Somewhat satisfied”	“Very satisfied” only
Reduction in rescue SSA use	“Less frequent”	N/A
Reduction in dose of long-acting SSAs	“Decreased”	N/A
Reduction in frequency of long-acting SSA injection	“Decreased”	N/A
Improvement in overall CS symptom control based on PGIC	“Very much improved”, “Much improved”, or “Somewhat improved”	“Very much improved” or “Much improved” only
WPAI-SHP		
Reduction in absenteeism	[REDACTED]	N/A
Reduction in presenteeism	[REDACTED]	N/A
Reduction in activity impairment	[REDACTED]	N/A
Reduction in overall productivity loss	[REDACTED]	N/A
Weight gain	[REDACTED]	N/A

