Common side effects of SSAs are back pain, fatigue, headache, abdominal pain, nausea, and dizziness. Other side effects identified include biliary tract abnormalities (jaundice, gallstones, sludge, and dilatation), hyper- or hypoglycemia, hypothyroidism, and cardiac changes (sinus bradycardia, conduction abnormalities, and arrhythmias) (Novartis Pharmaceuticals Corp., Sandostatin® LAR Depot package insert, 2016).

Recently, results from the PROMID and CLARINET studies demonstrated the antiproliferative effects of octreotide and lanreotide autogel® (Caplin, 2014; Rinke, 2009).

Therefore, use of SSAs to reduce tumor proliferation has become increasingly common in the treatment paradigm for many patients with NET with or without symptoms.

In a substantial number of NET patients with CS, a tachyphylaxis to SSA treatment may occur as soon as 1 week and as long as 12.5 months after starting therapy (Garland, 2003; Moertel, 1987), possibly due to desensitization of the SSAs' effect on the somatostatin receptors (Hofland, 2003). This desensitization to SSAs may be overcome in some patients by increasing the dosage of SSA above the approved label; however, the efficacy and safety of higher doses is not yet established (Broder, 2015). Significant tumor progression might also contribute to the decrease in efficacy of SSAs over time.

Patients whose symptoms are generally controlled using long-acting SSA therapy may require supplemental doses of short acting SSA therapy when symptoms become exacerbated. Results of a 93 patient study with octreotide indicate approximately 35% to 40% of the patients who received the long-acting release (LAR) Depot formulation still require supplemental subcutaneous (rescue) therapy to control exacerbation of CS symptoms. After 6 months of treatment with octreotide, the number of patients requiring "rescue" doses increased to approximately 50% to 70% of patients. When a patient's response to SSA therapy declines, it is accepted practice to continue SSA therapy while initiating additional treatments, including additional prescribed and over the counter medications (Öberg, 2004).

Surgical debulking of tumors, radiation, various liver directed therapies, and chemotherapy may be attempted as a way of addressing overall tumor burden and reducing associated serotonin production (Kulke, 1999; Kulke, 2011; Öberg, 2012; Turaga, 2011).

Scientific Background for Development of XERMELO

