Given the established role of serotonin in CS, inhibiting activity of tryptophan hydroxylase (TPH), the rate limiting enzyme responsible for the production of serotonin, should ameliorate symptoms and could perhaps avoid longer term disease sequelae.

XERMELO is a tryptophan hydroxylase inhibitor indicated for the treatment of carcinoid syndrome diarrhea in combination with SSA therapy in adults inadequately controlled by SSA therapy. Through inhibition of tryptophan hydroxylase, XERMELO reduces the production of peripheral serotonin, and the frequency of carcinoid syndrome diarrhea (Lexicon Pharmaceuticals, Inc., XERMELO™ package insert, 2017).

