6.1 Inclusion Criteria

Patients must meet all of the following criteria to be considered eligible to participate in the study:

1. Adult, ≥ 18 years of age at the time of informed consent
2. A new, valid prescription for XERMELO
3. Initiating XERMELO for the treatment of carcinoid syndrome
4. Able and willing to provide informed consent prior to participation in the study

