3.2 Variables for Analysis

3.2.1 *Demographics, Medical History, and Change in Weight*

Several demographic and medical history variables will be collected as part of the Baseline questionnaire. These include:

- Age and sex
- Highest level of education
- Race and ethnicity
- Geographic region
- Height (in feet and inches) and weight (in pounds)
- Diagnosis date for CS
- Site and diagnosis date of primary NET causing CS

Patients will also be asked to qualitatively assess their weight change since initiating XERMELO at each 6-month Follow-up ("I weigh less," "I weigh about the same," "I weigh more," "I don't know").

3.2.2 *Prior and Concomitant Treatments for Carcinoid Syndrome*

Patients' use of other treatments for CS, specified below, will be assessed at Baseline and/or at each 6-month Follow-up:

- Recent or concomitant use of short-acting or long-acting somatostatin analog medications at Baseline
- Changes in SSA use (frequency and dose) at each Follow-up
- NET-related surgery for CS within 6 months of Baseline and the reason for the surgery

- Additional concomitant treatments for CS (radionuclide therapy, radiation, chemotherapy, embolization, chemoembolization directly into liver)

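### The three SSA-reduction endpoints take their denominator from the month-6 answer alone; unless non-users skip the item or answer *Not applicable*, they count as non-reducers, so the main denominator should be Baseline users of that SSA

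*SAP*

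**What the plan says.** **Who is in the study.** Protocol 6.1 asks for a patient "Initiating XERMELO for the treatment of carcinoid syndrome", with adult age, a new prescription and consent. Neither 6.1 nor 6.2 mentions SSA use. The analysis population (Protocol 10.2, SAP 5.1.2) adds no SSA condition.

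**How the endpoints are defined.** SAP 5.1.4 states: "For estimation of the proportions for the primary and secondary endpoints, patients will be categorized based on their responses to the corresponding questionnaire items". Table 1 then counts a patient as having reduced if the answer is *Less frequent* (rescue SSA use) or *Decreased* (long-acting dose; long-acting frequency). No denominator of users is named.

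**What is left out of the denominator.** SAP 5.1.4 removes *Not applicable* responses from each proportion. SAP 5.1.1 removes missing and *Prefer not to answer* responses, and SAP 5.2 confirms that nothing is imputed for secondary endpoints. SAP 3.2.3 describes a *Not applicable* option for the diarrhea and flushing satisfaction items. SAP 3.2.2, which covers SSA, lists no response options. Protocol 8.2.1.2 has patients describe SSA changes where that applies to them.

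**What is available.** SAP 3.2.2 collects "Recent or concomitant use of short-acting or long-acting somatostatin analog medications at Baseline". Protocol 8.2.2.4 sets the Baseline window at 1 month.

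**The concern.** A reduction is possible only for someone who was using the drug. A patient with no rescue SSA at Baseline and none at month 6 could truthfully report no change. If the item accepts that answer, the patient enters the denominator as a non-reducer. The proportion then mixes two quantities: how many patients use the SSA, and how many users cut back. Only the second describes SSA reduction after starting XERMELO.

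The *Not applicable* route is not a full remedy even if it is offered. It is chosen by the patient at month 6 and is not tied to Baseline use. A Baseline rescue user who has stopped altogether might choose it and be dropped, although that is the largest reduction possible. A Baseline non-user who has since started an SSA could stay in.

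**Working it through.** **1. The plan's own figure.** SAP 2.4 concerns the primary endpoint: "Two-sided 95% confidence limits (CLs) will be calculated for this proportion using normal approximation", with an expected proportion of 50% and a precision of 5 points.
- n = z² p(1 − p)/w² = 1.96² × 0.25/0.05², which is 384.15 with unrounded z, so 385. This matches.
- For enrollment: "Assuming that 40% of the patients who participate in the study will drop out prior to the 6-month survey". 385/(1 − 0.40) = 641.7, so 642, against 643 stated. This matches to within one patient.

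This calculation is not affected by the present point. It supplies the 385 month-6 respondents used below.

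**2. What happens to a non-user under the SAP rules.**

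| Non-user's month-6 answer | In denominator? | Counted as |
|---|---|---|
| Item skipped or missing | No | – |
| *Prefer not to answer* | No | – |
| *Not applicable*, if offered | No | – |
| No-change type of answer, if possible | Yes | Non-reducer |

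Only the last row dilutes. The documents neither confirm nor rule it out.

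**3. Size if every non-user falls in the last row.** Let u be the share of respondents using the SSA and p the proportion of users who reduce. The reported proportion is u × p.

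The documents give neither u nor p for this study. For u, Protocol 3.1 reports from a 93-patient octreotide study that "approximately 35% to 40% of the patients who received the long-acting release (LAR) Depot formulation still require supplemental subcutaneous (rescue) therapy", rising to about 50–70% after 6 months. That is another population, used here only to set a range. Values of 50% and 30% for p are assumptions. The 95% half-width is 1.96 × √[q(1 − q)/m], where q is the proportion shown and m its denominator.

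Rescue SSA, 385 respondents:

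| u | Users (u × 385) | Reported if p = 50% | Reported if p = 30% (all 385) | Users only, p = 30% |
|---|---|---|---|---|
| 35% | 135 | 17.5% | 10.5% ± 3.1 | 30% ± 7.7 |
| 40% | 154 | 20% | 12.0% ± 3.2 | 30% ± 7.2 |
| 50% | 192 | 25% | 15.0% ± 3.6 | 30% ± 6.5 |
| 70% | 270 | 35% | 21.0% ± 4.1 | 30% ± 5.5 |

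For example, in the first row 0.35 × 0.50 = 17.5%, and 1.96 × √(0.30 × 0.70/135) = 7.7 points. The narrower limits in the all-respondent column surround a different quantity, so they are not a gain in precision on reduction among users.

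**4. Long-acting SSA.** Protocol 3.1 describes XERMELO as "indicated for the treatment of carcinoid syndrome diarrhea in combination with SSA therapy in adults inadequately controlled by SSA therapy", so most patients should be on an SSA. With u assumed at 90–100% and p = 30%, the reported figure is 27–30%.

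**5. Lower limit of the effect.** If all non-users fall in the first three rows of step 2, non-users cause no dilution.

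**The case against.** The strongest reply is that the SAP already deals with this. The sentence after the one quoted removes *Not applicable* from every proportion, missing answers are removed too, and Protocol 8.2.1.2 limits the SSA questions to patients to whom they apply. SAP 3.2.3 is about symptom items, so its silence on SSA items does not show that the option is absent. The survey items and the variable specification (SAP 5.1.1) are not in the documents.

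Much of this stands. A reader might infer that the plan will certainly understate SSA reduction, or that all three endpoints are badly affected. The documents do not support either reading: they do not show that a non-user can give a no-change answer, and labelled use makes many long-acting non-users unlikely. Nor do they support a claim that the figures would drift with case mix between yearly analyses.

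The reply does not close the gap, however. The where-applicable wording does not establish skip logic: Protocol 8.2.1.5 uses it for weight change, yet SAP 3.2.1 lists that item's options with no *Not applicable* among them. When Protocol 10.4.1 leaves the handling of that response to the SAP, it names only the diarrhea and flushing items.

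It is also fair that these are descriptive secondary proportions and that SSA use is tabulated at Baseline and changes at each follow-up (SAP 5.1.3.2). Those tables help, but none is specified that crosses Baseline use with the month-6 answer.

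A further objection concerns the remedy. Rescue SSA is intermittent, and an intermittent user with none in the 1-month Baseline window would leave the main analysis. That is a true cost, and it is the reason to keep the all-respondent figure.

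**Conclusion.** The point holds conditionally. SSA use is not required at entry, and the SAP sets the denominators of the three SSA endpoints by the month-6 answer without reference to Baseline use.

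- **Rescue SSA:** the reported proportion lies between no dilution and u × p. With assumed user shares of 35–70% and half of users reducing, the diluted extreme is 17.5–35% instead of 50%.
- **Long-acting SSA:** the effect is probably small.
- **Primary endpoint and sample size:** not affected.

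The lower limit of the effect is zero, and the response options that would settle where it lies are not shown. The change is still worth making, because a Baseline-user denominator gives an interpretable proportion whatever the item wording turns out to be.

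**What to change.** In SAP 5.1.4 and Table 1:

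1. Make the main denominator for reduction in rescue SSA use the patients who report short-acting SSA use at Baseline and have a month-6 response. For the two long-acting endpoints, use those reporting long-acting SSA use at Baseline with a month-6 response.
2. For rescue SSA use, count a Baseline user who has stopped as a reducer, and do not drop that patient through a *Not applicable* answer.
3. Report the denominator n beside each proportion.
4. Show Baseline non-users separately, including any who started that SSA by month 6.
5. Keep the all-respondent proportion as a supplement, and state the response options or skip logic of each SSA item.

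**Cost.** This needs SAP wording and a filter on a variable already collected. Limits widen: at a 35% user share and 30% reducing, about ±7.7 points on 135 users, against ±3.1 points around the diluted 10.5% on 385 respondents. Intermittent rescue users with no use in the 1-month Baseline window would contribute to the supplement only.
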